## 2.4 Study Timepoints

Detailed schedules of all study visits and procedures for all subjects (except VVC subjects) are presented in [Table 3](#) and detailed schedules of all study visits and procedures for VVC subjects are presented in [Table 4](#).

**Table 3 Schedule of Treatment Visits and Procedures (All Fungal Diseases Except VVC)**

PROCEDURE Visit	Screen a	BL/ D1 a	D2 (PK Only)	D3- D5	D7- D10	Study Day 14 and then Every 14 days during Tx	D42	D84 t	D90 u	D120	D180	EOT	Unsch. Visits	FU 1 b (6- WK)	FU 2- FU 3 b
Days (allowable window)	-1 (-3)	Prior to Tx		±2 d	±2 d	±2 d	±7 d	±7 d	±7 d	±14 d	±14 d	±3 d	AP	± 7d	AP
GENERAL															
Informed Consent	X														
Subject Enrollment and ID Assignment	X														
Medical History and Demographics	X														
Inclusion/Exclusion Criteria	X	X													
Pregnancy Test s	X												X		
Prior and Concomitant Medications	X													X	
Study Drug Dispensing c		X				X									
Study Drug Collection and Accountability Review						X							X	X	
Study Drug Dosing		X	X	X									X d		
Subject Diary Dispensing and Collection		X				X							X	X	
EFFICACY															
Targeted PE including S&S v	X	X				X	X d	X d	X e,f		X e,f	X d		X d	X f
Mycological Testing g,j	X d	X d				↔ X d →		X d	X e		X e	X d		X d	
Imaging h	X d,r						X d	X d	X e,f		X e,f	X d,i		X d,i	
Serological Testing j,k	X d	X d				↔ X d →	X d	X d	X e,f		X e,f	X d		X d	X f
Esophagoscopy l	X m						X l					X l	X l	X l	
Spyrometry	X f	X f					X f								
SGRQ	X e	X e							X e		X e	X e		X e	

PROCEDURE Visit	Screen a	BL/ D1 a	D2 (PK Only)	D3- D5	D7- D10	Study Day 14 and then Every 14 days during Tx	D42	D84 t	D90 u	D120	D180	EOT	Unsch. Visits	FU 1 b (6- WK)	FU 2- FU 3 b
Days (allowable window)	-1 (-3)	Prior to Tx		±2 d	±2 d	±2 d	±7 d	±7 d	±7 d	±14 d	±14 d	±3 d	AP	± 7d	AP
6-Minute Walk Test	X e	X e							X e		X e				
MRC Dyspnea Scale	X e	X e							X e		X e				
Assessment of Recurrence												X e			X
Subject Status (alive/ deceased)							X	X o	X e,f	X e,f	X e,f				
Assessment of Efficacy							X d	X d	X d			X d	X d	X d	X f
SAFETY															
Vital Signs	X	X										X p	X	X	
General Physical exam	X												X		X
Clinical Laboratory Safety Assessments	X					X n	X n	X n	X n,e	X n	X n,e	X	X n	X n	
AEs	X														X
PHARMACOKINETIC															
PK Assessments q			X	X	X										

Abbreviations: AE = adverse event; ABPA = allergic bronchopulmonary aspergillosis; AP = as applicable; CPA=chronic pulmonary aspergillosis; d = day; D = Day; EC=esophageal candidiasis; eCRF=electronica case report form; EOT = End of Treatment; FU = Follow-up; ID = identification; IPA = invasive pulmonary aspergillosis; MRC = Medical Research Council; PK=pharmacokinetic; Screen. = Screening; S&S = signs and symptoms; SGRQ = St. George's Respiratory Questionnaire; Tx = treatment; Unsch. = unscheduled; W = Week.

Note: Study days, weeks and months are counted relative to the first dose of study drug (Baseline [Day 1]). For FU visits, weeks, months and years are counted relative to the EOT visit.

- a. Screening and Baseline (Day 1) may occur on the same day.
- b. FU visits will occur 6 weeks (6-Week FU = FU 1), 3 months (3-Month FU = FU 2) and 6 months (6-Month FU = FU 3) after the EOT visit. FU visits FU 2 and FU 3 will be conducted for ABPA subjects only.
- c. For subjects who are not hospitalized.
- d. As applicable based on fungal disease.
- e. For CPA subjects. Efficacy procedures for CPA subjects will be performed every 3 months following Day 180 if the subject is still on treatment.
- f. For ABPA subjects. Efficacy procedures for ABPA subjects will be performed every 3 months following Day 180 if the subject is still on treatment.
- g. For urinary tract infections, urine samples for fungal cultures are recommended to be collected every 48-72 hours until negative.
- h. In addition to the scheduled time points, imaging scans will be collected anytime during therapy, as clinically indicated.
- i. The window for EOT imaging may range from ± 3 to ± 7 days, depending on fungal disease.

- r. Baseline radiological assessments for invasive fungal disease should be performed ideally within 72 hours of Screening. However, assessments performed up to 7 days before/after the first administration of study medication may be used to confirm the diagnosis of the fungal disease if none exists within the ideal window.
- s. Pregnancy tests may be conducted more often (e.g., on a monthly basis), per local regulations.
- t. For CMC D84 is TOC unless EOT occurs first
- u. For CPA and ABPA D90 is TOC unless EOT occurs first
- v. Targeted Physical Examinations (clinical evaluation of signs and symptoms) should be performed if subject comes in for PK assessments

**Table 4 Schedule of Treatment Visits and Study Procedures for VVC**

Study Visit/ Day	Screen a	BL/ Day 1 a	D4	EOT D7	TOC D17	25- DAY FU D32 b	35- DAY FU c D42	Unsc h Visits
Study Procedures	-1 (-3)	Prior to Tx		Phone/ On-site c	± 3 days		Phone/ On- site c	
GENERAL								
Informed Consent	X							
Subject Enrollment and ID Assignment	X							
Medical History and Demographics	X							
Inclusion/Exclusion Criteria	X	X						
Pregnancy Test	X							
Prior and Concomitant Medications	X----- X							X
Study Drug Dispensing		X						
Study Drug Collection and Review								
Subject Diary Dispensing and Collection		X			X			
EFFICACY								
Targeted PE including Clinical Evaluation of Signs and Symptoms of Infection	X	X		X	X	X	If applic. d	
Mycological Testing (fungal culture)	X	If applic. .		X	X	X	If applic. d	If applic. .
Assessment of Recurrence						X		
Subject Status (alive/ deceased)							X	
Assessment of Efficacy				X	X	X	X	
SAFETY								
Vital Signs	X	X		X				X
General Physical exam	X			X				
Clinical Laboratory Safety Assessments	X			X		X		If applic. .
Adverse events	X----- --X							
PHARMACOKINETIC								
PK Assessments e								

Study Visit/ Day	Screen a	BL/ Day 1 a	D4	EOT D7	TOC D17	25- DAY FU D32 b	35- DAY FU c D42	Unsc h Visits
Study Procedures	-1 (-3)	Prior to Tx		Phone/ On-site c	± 3 days		Phone/ On- site c	

Abbreviations: applic. = applicable; BL = Baseline; D = day; eCRF = electronic case report Form; EOT = end of treatment; FU = Follow-up; ID = identification; PE = physical exam; PK = pharmacokinetic; Screen = Screening; TOC = test of cure; Tx = treatment; Unsch. = unscheduled.

- a. Screening and Baseline/ Day 1 can occur on the same day.
- b. The 25-Day FU visit will occur on study Day 32 (i.e., 32 days after the first dose of study drug and 25 days after EOT).
- c. The 35-Day FU visit will occur on study Day 42 (i.e., 42 days after the first dose of study drug and 35 days after EOT). This will be a telephone call and only a full on-site visit if the subject is symptomatic.
- d. Vaginal examination and samples for mycological testing to be done if the subject is still symptomatic.
- e. For subjects who give consent, sparse PK samples for Population PK analysis should be collected during the following time windows between [REDACTED] [REDACTED]. The time of dosing and sample collection must be recorded on the subject diary and eCRF. Additional PK samples will be collected when clinically indicated.

### 3. General Statistical Considerations

Continuous data will be described using descriptive statistics (i.e. number of subjects, mean, standard deviation (SD), median, minimum, and maximum). Categorical data will be described using the subject count and percentage in each category. For the summary statistics of all numerical variables unless otherwise specified, minimum and maximum will be displayed to the same level of precision as reported. Mean and median will be displayed to one level of precision greater than the data collected. Standard deviation / standard error will be displayed to two levels of precision greater than the data collected. P-values will be rounded to three decimal places. If a p-value is less than 0.001 it will be reported as “<0.001.” If a p-value is greater than 0.999 it will be reported as “>0.999.” Data will be displayed in all listings sorted by disease category.

All analyses for ibrexafungerp will present the results by fungal disease, disease category ([Table 5](#)), and enrollment category. Overall response for global, clinical, and mycological responses will be presented for all disease categories combined.

Unless otherwise specified, baseline will be defined as the last non-missing assessment prior to or on the date (and time if appropriate) of the first dose of study drug. Change from baseline is defined as: post-baseline value – baseline value. For parameters measured over time, observed data and changes from baseline will be described for each time point.

The study day will be calculated as follows:

If the assessment date occurs on or after the date of the first dose of study drug:

Study day = assessment date – first dose date + 1.

If the date of interest occurs before the date of the first dose of study drug:

Study day = assessment date – first dose date

There is no study day 0.

All analyses will be conducted using SAS® Version 9.4 or higher. All statistical tests will be two-sided and interpreted at a 5% significance level.

#### 3.1 Determination of Sample Size

This is an exploratory study and no formal sample size calculations was performed. A total of 220 subjects (+10%) are estimated to be adequate for an assessment of the safety and tolerability of ibrexafungerp in subjects with documented eligible fungal diseases that have been refractory

to, resistant to, have relapsed after or subjects have intolerance to or demonstrated toxicities resulting from an approved SOC antifungal treatment.

### **3.2 Analysis Populations**

The analysis populations to be used in the analysis are defined as follows:

**Intent-to-Treat Population:** The intent-to-treat (ITT) population will include all subjects who are enrolled in the study and receive at least 1 dose of study drug.

**Myco-ITT:** the Myco-ITT population will include all ITT subjects with confirmed pathogens and who also had all necessary cultures or mycology tests to estimate mycological response.

**Per-Protocol Population:** The per-protocol (PP) population will include all ITT subjects who received enough study drug (ibrexafungerp) to enable clinical efficacy judgement as determined by the DRC, who have an EOT (TOC for VVC, CMC, CPA and ABPA as applicable) assessment and who have no major protocol violations that could impact the assessment of efficacy (Refer to Section 7).

**Safety Population:** The safety population will include all subjects who receive at least one dose of study medication and have at least one safety assessment post Baseline.

**Pharmacokinetic Population:** The pharmacokinetic (PK) population will include all enrolled subjects who provide at least one PK sample and no deviations significant enough to affect the interpretability of PK data.

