14.2.2.2 All Other Fungal Diseases Excluding Vulvovaginal Candidiasis

Mycological samples will be obtained for all subjects at Screening and/or Baseline/Day 1 (prior to treatment), and as applicable for each subject and fungal disease while on therapy. In addition, samples will be collected at the per-protocol visits displayed in [Table 10](#).

Table 10 Schedule of Visits for Mycological Assessments by Fungal Disease (Excluding VVC)

Study Days	D42	D84 ^b	D90 ^c	D180	EOT	Unsch. Visits	FU 1 (6-WK)	FU 2 & FU 3
Allowable window	±7 d	±7 d	±7 d	±14 d	±3 d	AP	± 7 d	AP
Acute or Chronic IC	X				X		X	
EC, OPC	X				X		X	
CMC^b	X	X			X		X	
D/I DF	X	X			X		X	
CPA^c			X	X ^a	X		X	
ABPA								
IPA	X	X			X		X	
Other emerging fungi	X	X			X		X	

Abbreviations: ABPA=allergic bronchopulmonary aspergillosis; AP = as applicable; CMC=chronic mucocutaneous candidiasis; CPA=chronic pulmonary aspergillosis; D=day; DF=dimorphic fungi; D/I= disseminated/ invasive; EC=esophageal candidiasis; EOT=end of treatment; FU=follow up; FU 1=6-Week FU; FU 2=3-Month FU; FU 3=6-Month FU; IC=invasive candidiasis; IPA=invasive pulmonary aspergillosis; OPC=oropharyngeal candidiasis; Tx=treatment; unsch.=unscheduled; VVC=vulvovaginal candidiasis; WK=week

Note: Mycological response will be assessed by fungal culture, KOH and other fungal stains, T2 testing, and serological testing (including, GMI, *Coccidioides* titers, and β-D-glucan levels, among others [Section 14.2.4]), if applicable.

a: Efficacy procedures for CPA subjects will be performed every 3 months following Day 180 if the subject is still on treatment.

b: For CMC subjects, D84 is TOC visit, unless EOT occurs first

c: For CPA and ABPA subjects, D90 is TOC visit unless EOT occurs first

14.2.2.2.1 *Candida* Infections Excluding VVC

Blood cultures: Two sets of blood cultures will be collected at Screening and repeated daily or every other day until blood cultures are negative for at least 48 hours (if it is only possible to obtain 1 set of blood cultures, a reason should be documented). Blood should be drawn peripherally [directly from a vein]; however, if this is not possible, blood may be drawn from a central IV catheter. Follow-up cultures will be performed as clinically indicated.

Non-blood cultures: Follow-up cultures from subjects who have non-blood sites of *Candida* infection should be performed as clinically indicated.

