EC: Follow-up KOH or fungal stains and/or mycological cultures from biopsy or brushing indicating yeast infection will be performed as clinically indicated.

OPC and CMC: Follow-up KOH or fungal stains and/or mycological cultures for *Candida* spp. obtained from the affected site will be performed as clinically indicated.

Urine cultures: for subjects with urinary tract infections, urine samples for fungal cultures are recommended to be collected every 48-72 hours until negative.

For subjects diagnosed exclusively by T2 testing:

- The diagnosis should be based on two consecutively positive T2 tests.
- For subjects diagnosed based on positive T2 tests, in addition to Screening, samples for T2 testing will be collected every 48 hours until negative.

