14.2.2.2 Other Fungal Diseases

Baseline mycological assessment (Screening) of the subject's fungal disease will be performed according to best local practice using local laboratories, including suitable samples for fungal culture and isolation as well as samples from the infected site for histology and cytology. Outside of these time points, mycological assessment will be performed as clinically indicated and/or in line with standard clinical management for the subject's specific fungal disease and anatomic site involved. The results of all mycological assessments, both culture and non-culture based (including negative results), performed during the study and relevant to the fungal infection will be recorded on the eCRF.

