Study Isolate	All fungal isolates recovered during study while the subject is receiving ibrexafungerp or during the follow-up window.	End of Study for each subject.

For subjects who are suspected to have a relapse of infection during the study follow-up period, cultures should be collected and other evaluations relevant to the signs and symptoms of infection should be performed before starting non-study antifungal therapy. Results of all mycological tests, including both culture and non-culture based (including negative results), relevant to the fungal infection under treatment should be documented on the eCRF.

Sites should make every attempt to save the initial isolate for the study. However, it is not mandatory to have the initial isolate for enrollment. In the absence of baseline isolates, all post-Baseline pathogens collected in the context of clinical failure and associated with the fungal disease will be stored and shipped to central laboratory for identification of fungal species and susceptibility testing. If the identities of the pathogens differ between the central and local laboratories, the central laboratory results will take precedence over the local results for all study purposes.

Other procedures and assessments will be performed as clinically indicated for the individual subject:

- Suitable samples for fungal culture and isolation (blood/ tissue cultures).
- Follow-up culture samples from non-bloodstream infections are not mandatory but, if obtained, results should be recorded. Histological or cytological findings are regarded as supportive evidence of invasive fungal disease and should be recorded, if available.
- For outcome assessment of fungal blood stream infections, confirmed (two consecutive) negative blood cultures are required.
- All isolates should be identified to species level. All baseline and EOT isolates will be stored and shipped for central retesting. The central laboratory results will be considered definitive.
- Biopsy/biological fluid samples from the infected site for histology and cytology.

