## 7. EFFICACY

The primary efficacy and secondary efficacy endpoints will be performed on the ITT, Myco-ITT and PP populations. The ITT analyses will be considered primary and the Myco-ITT and PP analysis will be considered supportive of the primary analyses on the ITT population.

The primary efficacy endpoint of the study is the percentage of subjects who achieve Global Response at TOC for VVC (Day 17), CMC (EOT or Day 84), CPA (EOT or Day 90) and ABPA (EOT or Day 90) (whichever comes first) and at EOT for all other diseases, as determined by the DRC. The primary efficacy endpoint will also be summarized by disease category and reason for enrollment separately. Secondary efficacy endpoints include the percentage of subjects who achieve Global Response, Clinical Response and Mycological Response by pathogen, fungal disease, disease category, and reason for enrollment at several time points as assessed by the DRC and by the Investigator. The following enrollment categories, as determined by the DRC unless stated otherwise, will be utilized: Refractory, Intolerant, Resistant (includes step-down cases), Toxicities, Relapse, Step-Down (as determined by PI). Each subject's enrollment reason will be validated by the DRC. The percentage of subjects with a recurrence, ACM and time to death will also be assessed.

Efficacy outcomes will be based on definitions captured in [Table 5](#) and [Table 6](#). Criteria for the DRC assessment of response will be further detailed in the DRC Charter. Criteria for the Investigator is outlined in [Section 7.2](#).

Efficacy evaluations will consist of clinical evaluations of the signs and symptoms of infection, mycological testing (including, but not limited to, fungal culture, KOH and other fungal stains, and T2 testing), imaging (e.g., CT, MRI, X-Ray or ultrasound) and serological testing (including, among others,  $\beta$ -D-glucan levels, GM and fungal antibody titers) as applicable for each fungal disease. Additional procedures (esophagoscopy, spirometry, St. George's Respiratory Questionnaire [SGRQ], 6-Minute Walk Test and Medical Research Council [MRC] Dyspnea Scale) will be conducted for selected fungal diseases.

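### Myco-ITT membership depends partly on mycology obtained after treatment starts, so the set can lose early deaths and subjects who were never re-sampled

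*SAP*

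**What the plan says.** SAP 3.2 limits Myco-ITT to ITT subjects who have a confirmed pathogen and "who also had all necessary cultures or mycology tests to estimate mycological response". The protocol synopsis and Protocol 18.2 carry the same definition. SAP 7 gives the set its use: "The primary efficacy and secondary efficacy endpoints will be performed on the ITT, Myco-ITT and PP populations". ITT is primary there, and Myco-ITT and PP are supportive. SAP 7.2 also reports the percentage surviving in Myco-ITT.

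The sampling rules behind the definition do not all agree:

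- Protocol 14.2.2.3 says "Follow-up culture samples from non-bloodstream infections are not mandatory but, if obtained, results should be recorded". For the bloodstream it says "For outcome assessment of fungal blood stream infections, confirmed (two consecutive) negative blood cultures are required".
- Protocol 14.2.2.2 leaves follow-up of non-blood *Candida* sites, EC, OPC and CMC to clinical indication; for OPC and CMC, samples "obtained from the affected site will be performed as clinically indicated". For other fungal diseases, outside the stated time points, "mycological assessment will be performed as clinically indicated and/or in line with standard clinical management".
- Against this, Protocol Table 10 schedules samples at EOT and the 6-Week FU for every non-VVC disease except ABPA, whose row is blank. Protocol 14.2.2.1 schedules VVC cultures at EOT, TOC and the 25-Day FU.

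SAP 7.2.3 defines presumed eradication and presumed persistence for subjects whose mycological documentation is missing, and maps presumed eradication to mycological success. It also has a category for no follow-up mycology at all.

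**The concern.** A set that carries the ITT label should be fixed by facts known at baseline, here a confirmed pathogen. The second condition asks for the tests needed to score a response, and response is assessed after dosing. Two kinds of subject can then leave the set: those who die, deteriorate or are lost before a follow-up sample, and those who improve and are not re-sampled. The first kind tends to raise the Myco-ITT response rate and the second to lower it.

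Survival is the clearest case. SAP Table 6 counts death in the evaluation period as a global failure whatever its cause. A subject who dies before any follow-up sample is a failure and a death in ITT, yet may be absent from Myco-ITT. Requiring a later test then selects for having lived long enough to be tested, which is an immortal-time type of selection.

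At stake is what the supportive analysis can show. If membership is related to outcome, agreement between Myco-ITT and ITT does not by itself confirm the ITT result, and disagreement does not by itself undermine it.

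**Working it through.** The documents give no expected size or response rate for Myco-ITT, so there is no stated figure to reproduce. What follows illustrates the selection effect.

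**Inputs**

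- N = 220, the planned enrolment (SAP 3.1). For simplicity, all are taken to have a confirmed pathogen.
- p = 11/20 = 55%, from the preliminary review of 20 subjects in Protocol 7.1. It serves only as a plausible rate. It gives 0.55 × 220 = 121 responders and 99 non-responders.
- qs and qf are the shares of responders and of non-responders with complete follow-up mycology. Both are assumptions; the documents give neither.

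**Formula**

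Myco-ITT rate = p·qs / (p·qs + (1 − p)·qf)

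Counts are rounded to whole subjects (exact halves to the even number). Intervals are 95% Clopper-Pearson, the method named in SAP 7.1.1.

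**Results**

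ITT reference: 121/220 = 55.0% (48.2 to 61.7).

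| qs / qf | Responders / Myco-ITT | Rate (95% CI) |
|---|---|---|
| 80% / 80% | 97/176 | 55.1% (47.4 to 62.6) |
| 90% / 90% | 109/198 | 55.1% (47.8 to 62.1) |
| 90% / 70% | 109/178 | 61.2% (53.7 to 68.4) |
| 90% / 60% | 109/168 | 64.9% (57.2 to 72.1) |
| 80% / 50% | 97/147 | 66.0% (57.7 to 73.6) |
| 70% / 90% | 85/174 | 48.9% (41.2 to 56.5) |
| 60% / 90% | 73/162 | 45.1% (37.2 to 53.1) |
| 50% / 80% | 60/139 | 43.2% (34.8 to 51.8) |

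Example, third row: 0.90 × 121 = 108.9, taken as 109; 0.70 × 99 = 69.3, taken as 69; 109/(109 + 69) = 61.2%.

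When qs equals qf, the formula returns p and there is no bias beyond rounding. When they differ, the rate moves towards the better-sampled group.

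**With membership fixed at baseline**

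In this simplified setting Myco-ITT coincides with ITT, 121/220 = 55.0%, whatever qs and qf are.

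**The case against.** The strongest reply is that the plan already limits the problem and that the consequence is small. Much of it stands.

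- **Sampling is not optional everywhere outside the bloodstream.** A reader might infer that it is from Protocol 14.2.2.3. The documents do not support that. VVC cultures are scheduled, Table 10 sets visits, T2 and β-D-glucan tests repeat until negative in subjects diagnosed by them, and mycological response can rest on *Aspergillus* IgG in CPA and on total IgE in ABPA. What the documents do show is that Table 10 and the text of 14.2.2.2 and 14.2.2.3 pull in different directions.
- **Discontinuation is partly covered.** Protocol 11.3 asks for EOT procedures (TOC procedures for VVC) from subjects who stop early, and for the 6-Week FU visit in non-VVC diseases. It cannot cover deaths, and non-VVC sampling stays subject to applicability by disease.
- **The presumed categories may bring subjects back in.** It is tempting to conclude that they cannot occur in Myco-ITT. That goes too far. If a presumed outcome makes response estimable, such subjects may qualify. The SAP leaves this open, and does not say which tests are necessary by disease or who decides.
- **The set is supportive.** The study is exploratory and single-arm, no decision rule uses Myco-ITT, and SAP 4.1 reports the size of each population by disease category. Those counts show how many subjects leave, but not why or with what ITT outcome.

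**Conclusion.** The point holds in a limited form. As written, Myco-ITT depends partly on post-baseline data, which can remove early deaths and subjects who were not re-sampled. This rests on reading the second condition as including follow-up tests. The definition does not use that word, but the reference to estimating response makes it the natural reading.

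The magnitude is not known. The range of about 43% to 66% around a 55% ITT rate comes from assumed sampling shares, not from trial data, and no bias arises if responders and non-responders are sampled equally. A reader might infer that Myco-ITT will overstate efficacy, or that its results cannot be interpreted at all. The documents support neither, because the direction cannot be known in advance.

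The primary ITT analysis is unaffected. What is exposed is the supportive efficacy analysis and the Myco-ITT survival percentages. The definition should be corrected, but the defect does not threaten the main result.

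**What to change.** 1. In SAP 3.2, the protocol synopsis and Protocol 18.2, define Myco-ITT as *every ITT subject whose baseline pathogen is confirmed by culture, by histology or cytology, or by another mycological test accepted in Protocol Table 5 (Eligible Fungal Diseases)*. Name the protocol in that reference, because Table 5 of the SAP is the table of efficacy time points.
2. State how ABPA subjects without direct mycological evidence are classified, since the ABPA criteria can be met without culture or histology.
3. Keep subjects without follow-up mycology in the denominator, as presumed or not evaluable, and count deaths as global failures.
4. If the present set is wanted, keep it as a separately labelled *mycologically evaluable* subset. Say which tests are necessary for each disease and whether presumed outcomes qualify, and tabulate exclusions by reason and by ITT outcome.
5. Reconcile Protocol Table 10 with the text of 14.2.2.2 and 14.2.2.3 on follow-up sampling.
6. Align SAP 7.1.1, which gives the primary confidence interval in ITT and PP only, with SAP 7 and Protocol 18.4.3, which list ITT, Myco-ITT and PP.

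The cost is wording in both documents and one population flag on data already collected. The downside is that more not-evaluable outcomes will show in Myco-ITT.
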